## Safety Monitoring:

According to the buspirone package insert, common adverse events associated with the use of buspirone not seen at an equivalent incidence among placebo-treated patients include dizziness, nausea, headache, nervousness, lightheadedness, and excitement. Treatment-emergent adverse events in placebo-controlled clinical trials occurring at a rate of at least 1% of patients taking buspirone include tachycardia, drowsiness, insomnia, decreased concentration, anger/hostility, confusion, depression, blurred vision, dry mouth, abdominal/gastric distress, diarrhea, constipation, vomiting, musculoskeletal pain, numbness, paresthesia, incoordination, tremor, skin rash, fatigue, and sweating/clamminess. Adverse events will be collected via a structured side effect rating scale completed with the participant and their primary caregiver. This will include a list of adverse experiences that have been reported with buspirone at a rate greater than 1% including but not limited to dizziness, drowsiness, nausea, headache, nervousness, fatigue, insomnia, xerostomia, impaired concentration, hostility, confusion, blurred vision, diarrhea, abdominal pain, numbness, and weakness. Each of these side-effects plus any additional complaints will be rated at baseline on a 4-point scale by the caregiver as follows: 0 = none; 1 = mild; 2 =moderate; 3 = severe. This scale is similar to that used by the RUPP Autism Network. Suicidality will be assessed at each visit by directly asking the subject (when verbal skills are sufficient) and the caregiver about any thoughts or behaviors that directly or indirectly might indicate suicidality (e.g., morbid thoughts, self-injury, statements about life not worth living), when indicated by positive responses. At baseline, the Columbia-Suicide Severity Rating Scale (C-SSRS) will be administered per the instructions at www.cssrs.columbia/ed/clinical trials.html. The C-SSRS will also be administered at each subsequent visit following the first report of suicidality. Subjects and caregivers will also have information on how to contact the on-call physician from our practice group who provides coverage 24 hours/day and 365 days/year. Physicians taking call are familiar with research protocols and can contact the principal investigator at any time.

All adverse events picked up on the rating scale as new will be recorded by the physician. The physician will also ask about any visits to the doctor, new medication use (e.g. OTC cold medicine), or any other complaints, in order to be confident that most adverse events are uncovered. The physician will keep a running log of adverse events that will record the date of onset, date of resolution, seriousness, severity, and relationship to study intervention

(e.g., definite, probable, possible, remote, or none) as well as whether the adverse event led to a change in study intervention or other treatment.

A physician will review vital signs as they become available. All significant adverse events as well as the progress of the study will be reviewed and discussed in detail at the biannual meetings of the **Data and Safety Monitoring Board (DSMB)**. The DSMB includes rotating members of MGH faculty and/or affiliates including physicians, researchers, and a biostatistician familiar with the study population and design. All serious or unexpected AEs that are possibly related to drug treatment will be reported to the MassGeneral Brigham IRB within 5 working days from notification of the event.

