We plan to provide preliminary evidence supporting the central hypothesis and accomplish the objectives of this study by pursuing the following specific aims:

- 1. Determine whether buspirone shows preliminary evidence of effectiveness, safety, and tolerability in children, adolescents, and adults with WS. This aim addresses our central hypothesis that buspirone will be effective and safe in the treatment of anxiety in persons with WS.
  - For preliminary evidence of effectiveness, we will require a significant decrease in mean PARS score from baseline and a ninety-five percent confidence interval for the effect size estimate consistent with a standardized effect size (difference in sixteen-week score from baseline divided by standard deviation at baseline) of one.
  - For preliminary evidence of safety, we will require no observation of serious or severe adverse effects possibly, probably, or definitely associated with buspirone.
  - For preliminary evidence of tolerability, we will require that the 95% confidence interval for dropout rate due to side effects of the drug be consistent with a rate of 20% or exclude values >=20%.
- 2. Determine which semi-structured interviews and existing anxiety rating scales would be most useful for characterizing participants and assessing anxiety treatment effects. A variety of outcome measures of anxiety will be used to better assess their applicability and feasibility in the WS population. The relative performance of the scales will be evaluated based on their sensitivity to change, their percent of item-level missing data, and any feedback on the appropriateness or ease of use of the scales from participants or study personnel.

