## **Inclusion Criteria:**

- 1. Age 5 to 65 years of age
- 2. **Diagnosis of WS** confirmed via genetic testing or a clinical diagnosis made by a clinician with significant experience treating patients with WS
- 3. Clinically significant anxiety as evidenced by a Pediatric Anxiety Rating Scale (PARS) score of 10 or greater (5-item scale). The PARS ("The Pediatric Anxiety Rating Scale (PARS): Development and psychometric properties." 2002) was chosen as an inclusion criterion (and outcome measure) since it assesses severity across common anxiety disorders in children including generalized anxiety, social anxiety, separation anxiety, and transition-associated anxiety. In addition, it is an instrument that allows the clinician to incorporate both child and parent report into a final clinician-rated score for each item.
- 4. A Clinical Global Impression Severity Item score ≥ 4 (moderate) for anxiety symptoms at Screen and Baseline.

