#### Sample Size Considerations:

Taking into account a likely placebo response, we consider a clinically meaningful decrease in mean PARS score 16 weeks after the start of buspirone to be equivalent to a standardized effect size (mean change/baseline standard deviation) of 1.0. Assuming a standardized effect size of 1.0, a correlation between baseline and week 16 measurements of 0.5, and a total loss to follow up of 30% (resulting in 14 participants providing complete data), a sample size of 20 participants provides greater than 90% power to detect a decrease in mean PARS score from baseline. In addition, for a standardized effect size of 0.2, a sample size of 20 provides nearly 80% power to rule out an effect size as large as 1.0.

For safety outcomes, if there is a serious or severe adverse event associated with buspirone treatment in the population that occurs with a frequency of 10% or more, we will have an 85% or greater chance of observing it in the study and concluding there are safety concerns with buspirone use in the population, assuming at least 90% (n=18) of participants remain in the study long enough to experience the event.

For tolerability, for discontinuation rates due to side effects of 50% or greater, a sample size of 20 provides 80% power to detect a difference from 20%, assuming no more than 10% dropout for unrelated reasons (n=18). All sample size calculations assume two-sided testing with alpha=0.05.

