#### **Statistical Analysis Plan:**

Demographic and clinical characteristics of the sample will be tabulated using means (SDs) for continuous characteristics and clinical scale scores treated as continuous and frequencies and percents for categorical and ordinal variables.

Change in PARS 5-item total score between baseline and week 16 will provide our primary preliminary estimate of efficacy. To estimate changes in PARS score and all other clinical outcomes but the CGI-I between baseline and week 16, we will use repeated measures linear regression models, as implemented in PROC MIXED in SAS and fit using REML estimation, with repeated measurements of clinical scores as outcomes and time, in categories, as the predictor. Our primary interest will be only in the difference between baseline and week 16 scores, but all observed scores will be included as outcomes, given that partially observed scores may be informative for estimation. We will obtain an estimate of 16-week change and corresponding 95% CI using a contrast of the week 16 and baseline model parameters. A contrast of the same parameters will provide a statistical test of the null hypothesis that there was no change in outcome between baseline and 16 weeks. For the CGI-I, we will estimate the percentage who respond to treatment and corresponding 95% CI using the proportion of participants with CGI-I scores <=2 at 16 weeks. For this calculation, participants who withdrew prior 16 weeks due to side effects will be included as non-responders, and participants who withdrew for other reasons will be excluded. Sensitivity to change will be compared between scales using standardized effect sizes, calculated using the estimated 16-week change in each outcome divided by the SD of the outcome at baseline. We will also tabulate and compare the percent of item-level missing data for each scale.

Frequency of all side effects and adverse events and corresponding 95% CIs will be tabulated. Tolerance and corresponding 95% CI will be estimated using the proportion of participants who did not withdraw from the study before 16 weeks due to reasons other than side effects or an adverse event who discontinue treatment due to side effects or an adverse event. We will also use the 16-week study retention rate and corresponding 95% CI, calculated as the proportion of the participants enrolling in the study who remain in the study for 16 weeks, as a measure of feasibility.

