#### **Schedule of Measures:**

Table 1. Schedule of Measures		Treatment Phase							
Measure	Screen	Baseline	Week						
			2*	4	6*	8	10*	12	16
Parent Ratings [1]									
Demographics	Х								
PARS [2]	Х	Х		Х		Х		Х	Х
SCARED [3]		Х		Х		Х		Х	Х
CASI Anxiety [4]		Х		Х		Х		Х	Х
ABC-2 [5]		Х		Х		Х		Х	Х
PSQI [6]		Х		Х		Х		Х	Х
Subject Assessments									
Height, Weight	Х								
Urine Pregnancy Test [7]	Х								

PARS**	Х	Х		Х		Х		Х	Х
SCARED**		Х		Х		Х		Х	Х
Stanford-Binet-5 (SB-5),	Х								
WASI-II [8], or									
Developmental Profile-4 (DP-									
4)									
Treating Clinician									
WS Diagnosis [9]									
Diagnostic Exam including	Х								
medical/psychiatric History									
Health/Behavior Review	Х								
Adverse Effects Review		Х	Х	Х	Х	Х	Х	Х	Х
CGI-Severity [10]	Х	Х							Х
CGI-Improvement [11]				Х		Х		Х	Х
Suicide Assessment [12] /	X*	X*	Х	X*	Х	X*	Х	X*	X*
C-SSRS* [13]									
Concomitant Treatments	X	Х	X	X		Х	Х	X	X
Concomitant Medications	X	Х	X	X		Х	Х	Х	X
*Telephone Visit: [1] Parent or primary caretaker ratings: [2] PARS = Pediatric Anviety Pating Scale: [3]									

\*Telephone Visit; [1] Parent or primary caretaker ratings; [2] PARS = Pediatric Anxiety Rating Scale; [3] SCARED = Screen for Child Anxiety Related Disorders; [4] CASI Anxiety = Child & Adolescent Symptom Inventory; [5] ABC-2 = Aberrant Behavior Checklist, Second Edition; [6] PSQI = Pittsburgh Sleep Quality Index; [7] Females of child-bearing potential only; [8] WASI-II = Weschler Abbreviated Scale of Intelligence, Second Edition; [9] genetic testing or clinical diagnosis; [10] CGI-S = Clinical Global Impression for Severity; [11] CGI-1 = Clinical Global Impression for Improvement [12] Suicide Assessment included in Adverse Effect Review; [13] Columbia-Suicide Severity Rating Scale (C-SSRS)\* will be administered to participant and/or parent if any positive suicidal ideation is reported during clinical assessment. Each visit following the first report of suicidal ideation will include the administration of the C-SSRS.; \*\* when subject's communication abilities allows

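### Could a severe worsening of a symptom already present at baseline escape the adverse event log and the zero-event safety criterion?

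*Combined protocol and SAP*

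**What the plan says.** Safety Monitoring has the listed side effects, plus any further complaints, graded from none (0) to severe (3); each "will be rated at baseline on a 4-point scale by the caregiver". The recording sentence for that scale is: "All adverse events picked up on the rating scale as new will be recorded by the physician". The physician also asks about doctor visits, new medicines "or any other complaints, in order to be confident that most adverse events are uncovered", and keeps a running log with onset, resolution, seriousness, severity, relationship to treatment, and whether treatment was changed as a result.

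The Schedule of Measures lists an "Adverse Effects Review" at baseline and at weeks 2, 4, 6, 8, 10, 12 and 16.

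For safety, Specific Aims (Aim 1) states: "we will require no observation of serious or severe adverse effects possibly, probably, or definitely associated with buspirone". Sample Size Considerations says of an event with a frequency of 10% or more that "we will have an 85% or greater chance of observing it in the study", with 18 participants remaining long enough. The Statistical Analysis Plan adds: "Frequency of all side effects and adverse events and corresponding 95% CIs will be tabulated".

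**The concern.** The word *new* is undefined, and nothing in the plan says how an increase from a non-zero baseline grade is classed. If new is taken to mean absent at baseline, a symptom graded 1 before treatment and 3 on treatment would not have to be recorded from the scale. It might then receive no relationship rating, because relationship appears only as a field of the log.

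The population makes this more than a theoretical case. Entry requires a PARS score of at least 10 and at least moderate anxiety on the CGI-S at screening and baseline. Nervousness is named as a common buspirone effect, and insomnia and impaired concentration are also on the side effect list. All three could plausibly be present before the first dose.

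The stake is the safety conclusion. With a zero-event rule and 20 participants, a single classification decision can reverse it, and two physicians could in principle class the same worsening differently.

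**Working it through.** **Step 1: the plan's own figure.** Inputs from Sample Size Considerations: event rate p = 0.10, n = 18. The chance of at least one event is 1 − (1 − p)^n = 1 − 0.90^18 = 1 − 0.150 = 0.850. The stated 85% is reproduced.

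**Step 2: what under-recording would do.** Let u be the share of qualifying events that never reach the log. The chance becomes 1 − (1 − 0.10 × (1 − u))^18. The documents give no value for u; those below are assumptions.

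| u (assumed) | Effective rate | Chance of at least one recorded event |
|---|---|---|
| 0 | 0.100 | 1 − 0.900^18 = 0.850 |
| 0.10 | 0.090 | 1 − 0.910^18 = 0.817 |
| 0.25 | 0.075 | 1 − 0.925^18 = 0.754 |
| 0.50 | 0.050 | 1 − 0.950^18 = 0.603 |

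**Step 3: what u stands for.** It is a product, u = a × b. Here a is the share of qualifying events that are worsenings of a symptom already graded at baseline, and b is the probability that such a worsening is missed by every recording route. As an illustration, u = 0.25 needs a = 0.5 and b = 0.5: half of all qualifying events would have to be worsenings, and half of those would have to pass unlogged although severe. For an event usually absent at baseline, a is near 0 and the 85% is untouched.

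**Step 4: how large b can reasonably be.** The relevant provisions, taken together:

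- The recording sentence says what is to be captured from the scale. It does not say that anything else is to be left out.
- Identifying something on the scale as new makes sense only if the scale is used again after baseline and compared with the baseline rating. Repeat use and a purpose for the baseline grades are therefore implied, and seven post-baseline reviews provide the occasions.
- The open enquiry and the running log are not limited to symptoms absent at baseline. A symptom that has become severe is a complaint on any ordinary reading.
- The Aim 1 criterion turns on observing a serious or severe related effect, and the tables cover all side effects and adverse events. Neither is restricted to new symptoms.
- Serious events that are possibly related have their own reporting route to the IRB, so the serious half of the criterion is little exposed.
- Dosing depends on tolerability, so the physician has to ask how symptoms are being borne. For nervousness in particular, the PARS, SCARED, CASI Anxiety items and CGI-I are all collected at weeks 4, 8, 12 and 16.

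What remains is a severe but non-serious worsening that nobody raises at any of seven reviews and that prompts no doctor visit or new medicine. That points to a small b, although the documents do not allow it to be estimated.

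**The case for a change.** The strongest case for a change is that none of these routes states a rule for worsening. The open enquiry is said to give confidence that most events are found, not all. The anxiety scales are efficacy measures, and nothing sends a worse score to the adverse event log. IRB reporting covers serious or unexpected events, and a severe, non-serious worsening of a listed symptom may be neither. In an open-label study with a zero-event criterion, it is better to settle what counts before data arrive than afterwards, and doing so takes two or three sentences.

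Part of this stands. The definition is missing, and physicians could differ over marginal cases such as a one-grade rise. It does not follow that a severe worsening on drug falls outside the plan: that reading requires one sentence to be taken in isolation from the log, the enquiry and the criterion around it. A fixed rule also has a price. If every one-grade rise were logged, then with no control arm a fluctuation from moderate to severe in a pre-existing symptom, judged possibly related, would by itself fail the safety criterion. A one-grade threshold is one convention among several and is not clearly better than the physician's judgement, recorded with severity and relationship.

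**Conclusion.** No change to the plan is needed. The ambiguity over *new* is real but is a matter of unwritten detail. A study physician following the rest of the safety section would ordinarily log a mild-to-severe worsening on treatment with its severity and relationship, and it would then count towards the Aim 1 criterion and the safety tables. No stated figure is wrong: the 85% stands as 1 − 0.9^18 = 0.850. The lower values of 81.7%, 75.4% and 60.3% rest wholly on assumed unrecorded shares of 10%, 25% and 50%, which nothing in the documents supports.

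The conclusion assumes that the side effect scale is used again at the scheduled reviews and compared with baseline, as the recording sentence implies. It also assumes that the physician treats a symptom that has become severe on drug as an adverse event.

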#### Sample Size Considerations:

Taking into account a likely placebo response, we consider a clinically meaningful decrease in mean PARS score 16 weeks after the start of buspirone to be equivalent to a standardized effect size (mean change/baseline standard deviation) of 1.0. Assuming a standardized effect size of 1.0, a correlation between baseline and week 16 measurements of 0.5, and a total loss to follow up of 30% (resulting in 14 participants providing complete data), a sample size of 20 participants provides greater than 90% power to detect a decrease in mean PARS score from baseline. In addition, for a standardized effect size of 0.2, a sample size of 20 provides nearly 80% power to rule out an effect size as large as 1.0.

For safety outcomes, if there is a serious or severe adverse event associated with buspirone treatment in the population that occurs with a frequency of 10% or more, we will have an 85% or greater chance of observing it in the study and concluding there are safety concerns with buspirone use in the population, assuming at least 90% (n=18) of participants remain in the study long enough to experience the event.

For tolerability, for discontinuation rates due to side effects of 50% or greater, a sample size of 20 provides 80% power to detect a difference from 20%, assuming no more than 10% dropout for unrelated reasons (n=18). All sample size calculations assume two-sided testing with alpha=0.05.

#### **Statistical Analysis Plan:**

Demographic and clinical characteristics of the sample will be tabulated using means (SDs) for continuous characteristics and clinical scale scores treated as continuous and frequencies and percents for categorical and ordinal variables.

Change in PARS 5-item total score between baseline and week 16 will provide our primary preliminary estimate of efficacy. To estimate changes in PARS score and all other clinical outcomes but the CGI-I between baseline and week 16, we will use repeated measures linear regression models, as implemented in PROC MIXED in SAS and fit using REML estimation, with repeated measurements of clinical scores as outcomes and time, in categories, as the predictor. Our primary interest will be only in the difference between baseline and week 16 scores, but all observed scores will be included as outcomes, given that partially observed scores may be informative for estimation. We will obtain an estimate of 16-week change and corresponding 95% CI using a contrast of the week 16 and baseline model parameters. A contrast of the same parameters will provide a statistical test of the null hypothesis that there was no change in outcome between baseline and 16 weeks. For the CGI-I, we will estimate the percentage who respond to treatment and corresponding 95% CI using the proportion of participants with CGI-I scores <=2 at 16 weeks. For this calculation, participants who withdrew prior 16 weeks due to side effects will be included as non-responders, and participants who withdrew for other reasons will be excluded. Sensitivity to change will be compared between scales using standardized effect sizes, calculated using the estimated 16-week change in each outcome divided by the SD of the outcome at baseline. We will also tabulate and compare the percent of item-level missing data for each scale.

Frequency of all side effects and adverse events and corresponding 95% CIs will be tabulated. Tolerance and corresponding 95% CI will be estimated using the proportion of participants who did not withdraw from the study before 16 weeks due to reasons other than side effects or an adverse event who discontinue treatment due to side effects or an adverse event. We will also use the 16-week study retention rate and corresponding 95% CI, calculated as the proportion of the participants enrolling in the study who remain in the study for 16 weeks, as a measure of feasibility.

Confidence intervals for binomial proportions will be calculated using Wilson's method. Confidence intervals and statistical tests will be two-sided, with test-wise alpha=0.05.

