- 6. Clinical Global Impressions (CGI). A trained clinician will perform the CGI. The CGI is designed to take into account all factors to arrive at an assessment of severity and response to treatment, including parent report, parent-rated measures, and clinician-rated measures (as described below). The CGI Severity (CGI-S) item is rated on a scale from 1 to 7 (1 = normal, not at all ill; 2 = borderline ill; 3 = mildly ill; 4 = moderately ill; 5 = markedly ill; 6 = severely ill; 7 = among the most extremely ill patients). The CGI Global Improvement (CGI-I) item is also rated from 1 to 7 (1 = very much improved; 2 = much improved; 3 = minimally improved; 4 = no change; 5 = minimally worse; 6 = much worse; 7 = very much worse). Subjects receiving a CGI-I rating of 1 or 2 will be classified as **responders** to treatment. The severity ratings will be conducted at screen, baseline and the last follow-up visit. The improvement ratings will be conducted at each follow-up visit.

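### The CGI-I responder rate drops lack-of-benefit withdrawals from its denominator, which biases this secondary, descriptive rate upward to the extent that such withdrawals occur

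*Combined protocol and SAP*

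**What the plan says.** The Statistical Analysis Plan defines the CGI-I responder rate as the proportion scoring 2 or less at week 16, with a Wilson 95% interval. Withdrawals due to side effects stay in the denominator as non-responders; "participants who withdrew for other reasons will be excluded". The documents do not break these other reasons down.

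The other outcomes are handled differently. The mixed model covers PARS and "all other clinical outcomes but the CGI-I between baseline and week 16", and it uses every observed score "given that partially observed scores may be informative for estimation". On the CGI-I, Outcome Measures (item 6) says: "The improvement ratings will be conducted at each follow-up visit". Table 1 places these ratings at weeks 4, 8, 12 and 16, but only week 16 enters the responder rate.

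In the same section, the tolerability proportion concerns participants "who discontinue treatment due to side effects or an adverse event", a wider grouping than the side effects named in the CGI-I rule.

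Sample Size Considerations gives two attrition figures. The PARS power calculation assumes "a total loss to follow up of 30" per cent, and the tolerability calculation is made "assuming no more than 10% dropout for unrelated reasons (n=18").

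**The concern.** The plan already treats one form of treatment failure, intolerance, as non-response. Leaving because the drug did not work is at least as direct a failure, yet it falls into the excluded group. If participants leave for that reason, the reported percentage describes a denominator from which some failures have been removed.

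Nothing else in the plan repairs this. The CGI-I is outside the mixed model, earlier CGI-I ratings are unused, and no sensitivity analysis of the rate is planned. The retention rate is a feasibility measure and does not adjust the responder rate.

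What is at stake is an easily quoted percentage from a single-arm, open-label pilot that is meant to precede a randomized trial. The Wilson interval reflects sampling error and not selective exclusion.

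**Working it through.** **The plan's own figure.** The 30% loss comes from the PARS power statement. With effect size 1.0 and correlation 0.5, the SD of change is √(2 × (1 − 0.5)) = 1.0 baseline SD. With n = 20 × 0.7 = 14 and two-sided alpha 0.05, the paired t-test has 93.2% power, which agrees with the stated figure of more than 90%. The plan states no power, target or expected value for the CGI-I rate.

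**Inputs from the documents.** 20 participants; 14 completers and 6 losses (30%); at most 10% of 20 = 2 dropouts for unrelated reasons.

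**Assumptions.** 10 responders among the 14 completers. In case A, the 10% is read as 2 withdrawals for other reasons, leaving 4 for side effects. The 10% and 30% come from separate calculations, so combining them is itself an assumption. In case B, all 6 losses are for other reasons. That is 30% of 20, three times the 10% figure, so case B is an outer bound.

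**Formulas.** Let r = responders, s = side-effect losses, f = other leavers who left for lack of effect, g = other leavers who had improved.

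- Planned rate = r/(14 + s)
- Upward gap = r/(14 + s) − r/(14 + s + f)
- Downward gap = (r + g)/(14 + s + g) − r/(14 + s)

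**Case A (s = 4, r = 10).** Planned rate 10/18 = 55.6% (Wilson 33.7 to 75.4%, width 41.7 points).

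| Who the other leavers are | Rate counting them | Planned rate is |
|---|---|---|
| f = 1 | 10/19 = 52.6% (31.7 to 72.7%) | 2.9 points too high |
| f = 2 | 10/20 = 50.0% (29.9 to 70.1%) | 5.6 points too high |
| g = 1 | 11/19 = 57.9% | 2.3 points too low |
| g = 2 | 12/20 = 60.0% | 4.4 points too low |

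Varying the responder count with f = 2: r = 7 gives 38.9% − 35.0% = 3.9 points, and r = 12 gives 66.7% − 60.0% = 6.7 points.

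**Case B (s = 0, r = 10).** Planned rate 10/14 = 71.4% (45.4 to 88.3%).

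- f = 1: against 10/15 = 66.7%, 4.8 points too high
- f = 2: against 10/16 = 62.5%, 8.9 points too high
- f = 3: against 10/17 = 58.8%, 12.6 points too high
- f = 6: against 10/20 = 50.0%, 21.4 points too high
- g = 6: against 16/20 = 80.0%, 8.6 points too low

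Gaps are taken from unrounded percentages. If all 6 losses were due to side effects, nobody would be excluded and the gap would be zero.

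**The case against.** **The rule is prespecified and is not a plain completers' rate.** Side-effect leavers count as failures, retention among all enrolled is reported, and a reader could derive responders out of 20 from the planned outputs. Excluding truly unrelated withdrawals is also legitimate, since counting them as failures would bias the rate downward. All of this stands. It does not cover the participant who leaves because the drug did not help.

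**Worsening may already be counted.** A reader might infer that every withdrawal for worsening is dropped. The documents do not support that. The side-effect scale in Safety Monitoring includes nervousness, hostility and insomnia plus any further complaints, and the physician logs new events found on it. Some worsening could therefore be recorded as a side effect and counted as non-response. Only worsening not so recorded is lost; simple lack of benefit has no such route.

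**The size is small and assumed.** In case A the largest gap with 10 responders, 5.6 points, equals one participant's rating (1/18 = 5.6%). This stands, and it limits the point to a minor one.

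**The bias can run the other way.** If participants leave after improving, the planned rate is too low, as the working shows. This also stands.

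**The terminology is loose throughout.** The tolerability criterion in Specific Aims also speaks only of side effects, so the narrower wording in the CGI-I rule is an editorial matter, worth settling in the same edit.

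**Conclusion.** The point holds as a minor one. The CGI-I rule removes lack-of-benefit withdrawals, and any worsening not recorded as a side effect, from the denominator. The rate is then too high to the extent that such withdrawals occur. With 10 assumed responders and other-reason dropout at the plan's 10%, the gap is 2.9 or 5.6 points, against an interval about 42 points wide. The responder count and the split of withdrawal reasons are assumptions.

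Two stronger readings are not supported:

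- That the rate is known to be inflated by some 20 points. The 21.4-point figure needs all 6 losses to be for other reasons, three times the 10% assumption, and all 6 to be for lack of effect.
- That the trial's effectiveness conclusion is compromised. PARS is the primary outcome, and the Aim 1 criterion rests on it: "we will require a significant decrease in mean PARS score from baseline", together with an effect-size interval. Early leavers' PARS scores enter the mixed model. The CGI-I rate carries no test or threshold; it is descriptive and, though the plan does not use the word, secondary.

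**What to change.** Amend the CGI-I sentence in the Statistical Analysis Plan as follows:

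- Count withdrawals for side effects or an adverse event, or for lack of effect (including worsening), as non-responders.
- Keep all other withdrawals excluded from the main rate, and state explicitly that this includes participants who leave after improving.
- Record each withdrawal reason in these categories and tabulate them.
- Add one sensitivity proportion with all treated participants in the denominator, counting anyone without a week-16 CGI-I of 1 or 2 as a non-responder, and label it as a conservative bound.

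The cost is one SAP sentence, finer withdrawal-reason categories and one extra proportion. No new assessments are needed.

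There are downsides. The main rate may be lower, and it will depend on how withdrawal reasons are classified in an open-label trial. Leaving improved leavers out keeps the possible downward bias (4.4 points in case A if both had improved), which is why the rule should be explicit and the reasons tabulated. The bound can understate response: if those excluded would have responded at the reported rate, it reads 5.6 points low in case A (50.0% against 55.6%) and 21.4 points low in case B (50.0% against 71.4%). It should therefore not replace the main estimate.
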